6.5 Prior and Concomitant Therapy

Information about any treatments received in the 6 months prior to the date of informed consent and all the concomitant treatments given during the study (through follow-up period) with reason for the treatment will be collected by the investigator/authorised delegate at each visit (as shown in Table 1) and recorded in the eCRF.

In order to satisfy inclusion criterion 3, a history of long-term OCS therapy equivalent to a daily dose of at least 5 mg and up to 40 mg of prednisone/prednisolone for at least 3 months prior to Visit 1 should be documented in source and recorded in the eCRF.

In order to satisfy with inclusion criterion 2, a history of continuous treatment with high-dose ICS (high-dose ICS is the highest approved dose in a country) plus a LABA for at least 6 months prior to Visit 1 should be documented in source and recorded in the eCRF.

Use of ICS/LABA as a reliever (eg, Symbicort Maintenance and Reliever Treatment) that was part of the participant's usual asthma controller regimen at baseline is allowed; however, it should also be withheld before any morning cortisol and ACTH stimulation test as described in Section 8.2.1 and Appendix M. Any maintenance therapy (in addition to ICS/LABA) such as long-acting muscarinic antagonists used prior to study entry should not be changed during the study. The 'as-needed' use of short-acting BDs for relief of acute asthma symptoms is permitted throughout the study.

Asthma exacerbations should be treated with oral or other systemic corticosteroids according to standard practice (see Section 6.5.1.1).

Table 5 and Table 6 describe the concomitant medications allowed and prohibited during the study period.

Medications will be classified according to the World Health Organization (WHO) Drug Dictionary.

Before any morning cortisol or ACTH stimulation test is performed:

- Prednisone/prednisolone should not be taken at least 24 hours prior to morning cortisol level/ACTH stimulation test
- No high-dose ICS (or ICS/LABA if in single inhaler) treatment on the morning of the morning cortisol level/ACTH stimulation testing (for participants taking a once-daily ICS/LABA formulation, eg, fluticasone furoate/vilanterol, participants must not take the treatment ≤ 24 hours prior to the morning of the morning cortisol level/ACTH stimulation test).

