The visit should be rescheduled if the above medications are not withheld properly (note: short-acting β -agonist [SABA] rescue is allowed throughout the study).

 Table 5
 Restricted Medications

Medication/Class of drug	Usage
Maintenance treatment with ICS and long-acting BDs (including ICS/LABA combinations)	No changes in either dose or regimen are allowed from Visit 1 and throughout the IP treatment and preferably 4 weeks after the last dose of IP.
	The ICS (including ICS/LABA combinations) should be withheld the morning of any morning cortisol level/ACTH stimulation test. For participants taking a once-daily ICS/LABA formulation, eg, fluticasone furoate/vilanterol, participants must not take the treatment ≤ 24 hours prior to the morning of any morning cortisol level/ACTH stimulation test.
	Participants will not need a washout of their asthma medications for unscheduled visits due to asthma worsening.
Short-acting β-agonists	Regular scheduled use of SABA is not allowed from Visit 1 and throughout the IP treatment and preferably 4 weeks after the last dose of IP. Short-acting β-agonist rescue use is allowed if needed.

Additional maintenance controllers	Participants on theophyllines should have blood concentration levels within therapeutic range documented before proceeding in the study.
Inactive/killed vaccinations (eg, inactive influenza)	Allowed provided they are not administered within 5 days before or after any study visit.
Allergen immunotherapy	Allowed if participant has been receiving stable therapy for at least 30 days prior to Visit 1 and there is no anticipated change during the treatment period. Allergen immunotherapy should not be administered on the same day as study drug
Prednisone/prednisolone	Allowed provided it is not administered at least 24 hours prior to any morning cortisol/ACTH stimulation test
High-dose ICS (see Appendix I)	Allowed; however, ICS (or ICS/LABA if in single inhaler) treatment should not be administered on the same day as morning cortisol/ACTH stimulation test (for participants taking a once-daily ICS/LABA formulation, eg, fluticasone furoate/vilanterol; participants must not take the treatment the night prior or the morning of any morning cortisol/ACTH stimulation test).
Immunosuppressive medication	Topical or nasal administration may be allowed at the discretion of the investigator

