8.2.1 Hypothalamic-pituitary-adrenal Axis Evaluation

For all participants, HPA axis integrity will be evaluated after 4 weeks on 5 mg/day and prior to tapering down the OCS dose (for participants with baseline OCS doses equal to 5 mg/day, this will be assessed 4 weeks after the first dose of tezepelumab administration and before initiation of the OCS reduction phase).

First, a screening method with morning serum cortisol is done (8-9 am morning cortisol level), to evaluate whether the participant has:

- Normal cortisol levels (Table 9)
- Complete AI (Table 9).

Cortisol levels from the morning cortisol test that are below normal range and above the complete AI range are considered 'indeterminate' (Table 9), and require additional testing described below (for sites where tetracosactide is not available or not registered, please see Appendix M).

If the morning cortisol is in the indeterminate range, then the ACTH stimulation test is done within approximately 1 week (see Section 8.2.1.2 for details). The ACTH stimulation test is more specific than the morning cortisol test, and can determine whether the participant has:

- Normal cortisol levels: > 450 nmol/L (> 675 nmol/L for participants taking oestrogen-containing contraceptives)
- Complete AI: < 250 nmol/L (< 375 nmol/L for participants taking oestrogen-containing contraceptives)
- Partial AI: 250 to 450 nmol/L (375 to 675 nmol/L for participants taking oestrogen-containing contraceptives).

For morning serum cortisol and ACTH stimulation tests, hold OCS dose and other concomitant medications that could interfere with cortisol results as follows (see Section 6.5):

- The last OCS dose should be taken \geq 24 hours prior to testing
- Participants must not take ICS (or ICS/LABA if in single inhaler) treatment on the
 morning of the morning cortisol level/ACTH stimulation test (for participants taking a
 once-daily ICS/LABA formulation, eg, fluticasone furoate/vilanterol, participants must
 not take the treatment ≤ 24 hours prior to the morning of the morning cortisol
 level/ACTH stimulation test)
- If a participant requires a short course of macrolides, antivirals, or azoles, there must be a window of ≥ 1 week prior to the testing of cortisol levels.

The process will be as described in Figure 3.

[figure not shown]

Figure 3 Hypothalamic-pituitary-adrenal Axis Evaluation

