8.2.1.1 Morning Cortisol Test

The morning cortisol test will be done in all participants 4 weeks after reaching the 5 mg dose of OCS, and before further dose reductions. It is also done 3 months after a participant has completed a test indicating complete AI.

Serum samples for cortisol will be collected between 8 and 9 am and will be sent to a central laboratory for evaluation.

The following values will be used to define AI status for the morning cortisol test:

Table 9 Cortisol Status

AI status	SI units	Participants taking oestrogen- containing contraceptives
Normal	>350 nmol/L	>700 nmol/L
Indeterminate results	100 - 350 nmol/L	200 - 700 nmol/L
Complete AI	<100 nmol/L	<200 nmol/L

Once the results are available, the site will inform the participant of the results via telephone. For sites where tetracosactides are available, and depending on the result, the actions that will be implemented are as follows:

- If cortisol levels are within normal range and the participant does not exhibit any signs and/or symptoms of AI, the participant will continue OCS down-titration by 2.5 mg Q4W
- If cortisol levels are within normal range but the participant exhibits signs and/or symptoms of AI, then OCS down-titration should continue at a slower pace (1 mg Q4W).
- If cortisol levels are below the normal range and above the complete AI range (indeterminate result), then the participant will be instructed to maintain the current OCS dose and come back to the site within 1 week for an ACTH stimulation test (Section 8.2.1.2)
- If complete AI is confirmed, sites will inform participant that the OCS dose will remain the same without further reduction until there is evidence of recovery from the complete AI without worsening of asthma control. The morning cortisol test and associated clinical assessments (see Table 1) will be repeated 3 months later. After the repeat morning cortisol test, the site will inform the participant based on the results as follows:
 - If morning cortisol results indicate normal cortisol values, then reductions will be 2.5 mg Q4W, and the participant would subsequently move to maintenance at the OCS lowest possible dose
 - If morning cortisol results are indeterminate, then reductions will be delayed further, and the participant would return approximately 1 week later for an ACTH stimulation test:
 - o If normal result after ACTH stimulation (Table 10): reduce by 2.5 mg Q4W then move to maintenance at the lowest possible dose

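### The High-dose ICS row of Protocol Table 5 sets a looser withholding rule for once-daily ICS/LABA before cortisol testing than the 24-hour rule stated in three other places

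*Protocol*

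**What the plan says.** The Protocol states the rule for withholding a once-daily ICS/LABA product before a morning cortisol or ACTH stimulation test in four places.

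- **Section 6.5, bullet on preparation for testing:** "participants must not take the treatment ≤ 24 hours prior to the morning of the morning cortisol level/ACTH stimulation test".
- **Section 6.5, Table 5, first row (maintenance ICS and long-acting bronchodilators):** "participants must not take the treatment ≤ 24 hours prior to the morning of any morning cortisol level/ACTH stimulation test".
- **Section 8.2.1:** participants must "not take the treatment ≤ 24 hours prior to the morning of the morning cortisol" or ACTH test. The list containing this item opens with the instruction to "hold OCS dose and other concomitant medications that could interfere with cortisol results as follows".
- **Section 6.5, Table 5, High-dose ICS row:** "participants must not take the treatment the night prior or the morning of any morning cortisol/ACTH stimulation test".

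The first three give a 24-hour limit. The fourth gives no limit in hours.

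Two other statements matter. Section 8.2.1.1 fixes the sampling time: "Serum samples for cortisol will be collected between 8 and 9 am". Directly after the Section 6.5 bullets comes the consequence of a failed hold: "The visit should be rescheduled if the above medications are not withheld properly".

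**The concern.** The two rows sit in the same table, give the same example product and concern the same test, yet they bar different doses. The High-dose ICS row covers the preceding night and the test morning. It says nothing about the daytime of the day before, which the other three statements cover.

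A site that looks up inhaled steroids in Table 5 and stops at the High-dose ICS row could therefore go ahead with a test that Section 6.5 would have it reschedule. Section 6.5 also lists what is recorded for each medication (reason, start and end dates, dose and frequency). Clock time is not on that list, so such a dose might not be visible afterwards.

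The results of these tests have consequences. Under Sections 8.2.1.1 and 8.2.1.2 they decide whether the participant at 5 mg/day goes on in steps of 2.5 mg every 4 weeks, slows to 1 mg every 4 weeks, or stays put and is retested at 3 months. Under Section 8.1.1 a second result of complete adrenal insufficiency ends reduction for the rest of the trial. Where tetracosactide is not available, Appendix M classifies adrenal status from morning cortisol alone. In the SAP, adrenal status is an exploratory endpoint (Section 4.2.14) and a Week 52 subgroup factor (Section 4.2.1.7).

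**Working it through.** No published figure is at issue, so the check is a comparison of the rules followed by clock arithmetic.

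**Inputs**

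- 24-hour rule: Section 6.5 bullet, Table 5 first row, Section 8.2.1.
- Night-before and test-morning rule: Table 5, High-dose ICS row.
- Sampling window 08:00 to 09:00: Section 8.2.1.1.
- The Protocol does not say when the test morning begins for the 24-hour count, or when the night before begins. I count to the sample itself and, as an alternative assumption, to a morning starting at 06:00. For the start of the night I assume a range of 18:00 to 22:00.

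**Step 1: age of a dose taken the day before**

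Age = 24 h + anchor time − clock time of the dose.

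| Dose the day before | Age at 08:00–09:00 sample | Age at 06:00 (assumed) | High-dose ICS row | Other three places |
|---|---|---|---|---|
| 10:00 | 24 + 8 − 10 = 22 h to 24 + 9 − 10 = 23 h | 24 + 6 − 10 = 20 h | not barred | barred |
| 14:00 | 18 to 19 h | 16 h | not barred | barred |
| 16:00 | 16 to 17 h | 14 h | not barred | barred |

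Every age is within 24 hours on either count, and none of these doses falls in the night before or on the test morning.

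**Step 2: width of the gap**

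The gap runs from the time the 24-hour bar begins to the time the row's bar begins.

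- 08:00 sample: from 08:00 to 18:00–22:00, so 10 to 14 h.
- 09:00 sample: from 09:00 to 18:00–22:00, so 9 to 13 h.
- Counted to a 06:00 morning: from 06:00 to 18:00–22:00, so 12 to 16 h.
- Counted to a morning that starts at midnight: from 00:00 to 18:00–22:00, so 18 to 22 h.

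**Step 3: direction**

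Any pre-test dose that the High-dose ICS row bars is also barred by the other three. The reverse is not true. For doses before the test, the row is looser under every reading tried.

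**Step 4: after the change**

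With the 24-hour wording in the High-dose ICS row, all four statements bar the same pre-test window for once-daily products and the gap is 0 h.

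**The case against.** The strongest reply is that nothing in the Protocol actually permits the disputed dose. The High-dose ICS row is a prohibition that happens to be less complete, prohibitions accumulate, and a site that withholds for 24 hours complies with all four statements. The stricter rule also stands where a site should look first: in the testing section, in the bullets on test preparation, and in the Table 5 row whose label names ICS/LABA combinations. The rescheduling sentence enforces it. That stands, and it is why the point is minor. It does not remove the discrepancy: the Protocol states no order of precedence, and the High-dose ICS row is a natural place to look up an inhaled steroid.

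The affected group is also narrow, and this stands too. Evening dosers are barred everywhere. A habitual 07:00 dose the day before is 24 + 8 − 7 = 25 h to 24 + 9 − 7 = 26 h old at sampling and passes all four rules on that count, although counted to a 06:00 morning it is 23 h old and fails three of them. No consequence for results is demonstrated, and neither the sample size nor the primary analysis is touched.

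Finally, the main clause of the same row bars ICS on the day of the test, whereas the other places bar it on the morning of the test. In that respect the row is stricter, and changing the parenthesis leaves the difference in place. But the extra restriction concerns doses taken after the sample, which cannot affect it.

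**Conclusion.** The concern holds. It is a minor inconsistency in an operational rule, and three matching statements make clear that the 24-hour limit is the intended one. On the assumed start of the night (18:00 to 22:00), the High-dose ICS row leaves open 9 to 14 hours of the preceding day that the other places close, counting to the 8 to 9 am sample. The gap is wider if the 24 hours are counted to an earlier start of the morning.

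The error arises only at a site that follows this row alone, and only for once-daily users who dose in the daytime. The documents give neither the number of such users nor the size of any ICS effect on cortisol, so a changed adrenal class, taper step or endpoint result is possible but not shown. That the row is looser does not depend on the clock-time assumptions; only the width of the gap does.

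**What to change.** In the High-dose ICS row of Table 5, replace the parenthesis on once-daily products with the 24-hour wording of the table's first row, or with a reference to Section 8.2.1. Section 6.5 already uses that cross-reference for reliever ICS/LABA, where "it should also be withheld before any morning cortisol and ACTH stimulation test as described in Section 8.2.1 and Appendix M".

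This is one parenthesis in one table row. It needs no new data item and no change to the SAP. A few tests may have to be rescheduled, which Section 6.5 already provides for.

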6.5.1 Rescue Medicine

6.5.1.1 Management of Asthma Exacerbations During Treatment Period

Participants who experience an exacerbation during the treatment period may remain on the study drug at the investigator's discretion. Asthma exacerbations will be treated with oral or other systemic corticosteroids according to standard clinical practice.

- Induction phase: If a participant experiences an exacerbation during the induction phase, the start of the OCS dose reductions may be delayed. After the OCS bolus/burst to treat an exacerbation is complete, the participant may be returned to a one-step higher dose level (or more if considered necessary by the investigator) than what was prescribed when the exacerbation occurred. The investigator may decide to maintain the same OCS dose. The participant's OCS dose should be stable for at least 2 weeks before entering the OCS reduction phase
- Oral corticosteroids reduction and maintenance phase: If a participant experiences an exacerbation during the OCS reduction and maintenance phase, the investigator may do one of the following for at least 2 weeks after completion of the OCS bolus/burst:
 - The participant may be returned to a one-step higher dose level (or more if considered necessary by the investigator) than what was prescribed when the exacerbation occurred

or

 The same OCS dose may be maintained at a stable dosage and then OCS down-titration may be continued once the participant recovers from the exacerbation.

Further dose reductions during this phase will be considered as per the investigator's opinion (except from Week 48 onwards, when no further OCS dose reduction is allowed). After recovery from the first exacerbation, the participant will be allowed to proceed with another attempt to reduce their OCS dose; however, they would follow a lower speed of OCS down-titration (reductions Q4W; Table 8).

In case of a second exacerbation, no further OCS daily dose reduction will be allowed, and the participant will continue the same dose or will return to a one-step higher dose level (or more as considered necessary by the investigator) than what was prescribed when the exacerbation occurred. The participant will then continue the same dose through the end of the study.

6.5.1.2 Other Rescue Medicine

Rescue use of SABA administered via nebulisation is discouraged, except as urgent treatment during an asthma exacerbation.

6.5.2 Bronchial Thermoplasty

Participants should not be treated with bronchial thermoplasty during the study or for 12 months before Visit 1.

6.6 Dose Modification

Not applicable.

6.7 Intervention After the End of the Study

Participants who complete Visit 16 should be given standard of care, including commercially available tezepelumab, at the discretion of the investigator. In the UK, participants who complete the study are eligible to apply to the UK Tezspire¹ Patient Assistance Program for

¹ Tezepelumab trade name.

access to tezepelumab in case it is not yet commercially available.

7 DISCONTINUATION OF STUDY INTERVENTION AND PARTICIPANT DISCONTINUATION/WITHDRAWAL

7.1 Discontinuation of Study Intervention

It may be necessary for a participant to permanently discontinue (definitive discontinuation) tezepelumab.

Reasons for discontinuation of study intervention may include:

- Participant decision: The participant is at any time free to discontinue treatment, without prejudice to further treatment.
- Incorrectly enrolled/dosed participant in whom the inclusion/exclusion criteria violation would put the participant at undue risk.
- Adverse event for which the investigator judges continued treatment may put the participant at undue risk.
- Severe noncompliance with the Clinical Study Protocol (CSP).
- Pregnancy (see Section 8.3.11).
- Development of any study specific criteria for discontinuation, including:
 - An anaphylactic reaction to the IP requiring administration of epinephrine
 - A helminth parasitic infestation not responding to anti-helminth treatment
 - Any malignancy except participants who develop basal cell carcinoma or localised squamous cell carcinoma of the skin, provided that the malignancy is excised and determined to have clean margins.
- Development of one or more of the following:
 - Confirmed alanine aminotransferase (ALT) or aspartate aminotransferase
 (AST) increase of ≥ 8 × ULN
 - Confirmed ALT or AST increase of \geq 5 × ULN for more than 2 weeks
 - Confirmed ALT or AST increase of ≥ 3 × ULN and total bilirubin of ≥ 2 × ULN
 - ALT or AST of $\geq 3 \times$ ULN with the appearance of fatigue, nausea, vomiting, right upper quadrant pain or tenderness, fever, rash, and/or eosinophilia ($\geq 5\%$).

For discontinuation pertaining to COVID-19, please see Appendix C.

A participant who decides to discontinue study drug will always be asked about the reason(s)

and the presence of any AEs. The reason for premature discontinuation of tezepelumab should be documented in the source documentation and recorded in the eCRF.

All participants who prematurely discontinue study drug should:

- return to the study site and complete the procedures described for the IPD Visit within 4 weeks (± 7 days) after last tezepelumab administration,
- and have a follow-up visit 16 weeks after last tezepelumab administration (± 5 days) (see Table 1, Visit 16).

Participants who discontinue treatment should be encouraged to return for all regularly scheduled visits for safety and efficacy assessments.

At the IPD Visit the participants will be given the following 3 options as to how they will be followed:

- 1. The participant should be encouraged to return for all regular clinic visits and perform all scheduled assessments (excluding IP administration) until the EOT visit at Week 52 (± 5 days).
- 2. The participant will be offered follow-up on a monthly basis via telephone calls while continuing ePRO data collection on the handheld device at home (no further procedure will be performed) until the participant completes the on-site EOT visit at Week 52 (± 5 days).
- 3. If the participant cannot or does not wish to comply with any of the options above (or any component of them such as only telephone-based visits without completion of the ePRO data), the investigator will contact the participant via telephone at 52 weeks after baseline. No other study assessments will be performed prior to this contact.

Participants who discontinue IP with option 1 or 2 are allowed to further reduce their OCS dose following the same protocol-specified OCS dose reductions scheme as participants being still on-treatment.

If the last study intervention administration was after Week 36 for options 1 or 2, the participant will return to the clinic for an EOT visit at Week 52 (\pm 5 days). For option 3, the investigator will contact the participant at 52 weeks post baseline.

If a participant chooses option 1, all assessments will be completed as per the SoA as indicated in Table 1. If a participant chooses option 2 or 3, the key information to be collected during the telephone calls are AESIs/DAEs/SAEs, changes in concomitant medication, and asthma exacerbation information.

Participants who initially choose options 1 or 2 and subsequently cannot or do not wish to comply with the requirements of their option can continue with a less intensive option

(ie, participants initially choosing option 1 can continue with options 2 or 3, participants initially choosing option 2 can continue with option 3).

If a participant discontinues tezepelumab due to a study specific discontinuation criterion, this should always be recorded as 'Development of study specific discontinuation criteria' on the Discontinuation of IP form in the eCRF.

Note that discontinuation from study intervention is NOT the same as a withdrawal from the study. The EOT visit will be completed immediately in the case of subsequent early withdrawal from the study. Participants who do not wish to have any follow-up contacts will be discontinued from the study. All participants who withdraw from the study must return the ePRO at the EOT visit (and at IPD visit for participants choosing option 3 above).

